#### RETESTS, UNSCHEDULED VISITS AND EARLY TERMINATION DATA 6.4.

Unscheduled measurements will not be included in summary statistics but will contribute to the best/worst case value where required (e.g., shift tables) and assessment of clinical outliers.

\\ieedc-vnasc01\BIOSdata\Palladio\Lixivaptan\WYA34000\Biostatistics\Documentation\SAP\PA-Document:

102 SAP V1.0 NonPKPD 25APR2019 Author: [name]

1.0

25 April 2019 Version Date:

Version Number:

Template No: CS TP BS016 - Revision 5 Reference: CS WI BS005

Effective Date: 01Apr2018

Palladio Biosciences STATISTICAL ANALYSIS PLAN: PROTOCOL PA-102 Page 14 of 36

In the case of a retest of a scheduled assessment, the last available measurement for that scheduled time (i.e., the retest measurement) will be used for summaries unless flagged as invalid.

Listings will include all scheduled, unscheduled, retest and early discontinuation data.

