6.1 Safety and Tolerability Assessments

The safety and tolerability of lixivaptan will be assessed by evaluation of AEs, physical examinations, vital sign measurements, ECGs, clinical laboratory parameters (hematology, clinical chemistry including liver function tests, and urinalysis), and the questionnaire for tolerability. Additional safety assessments may be performed as needed at the discretion of the Investigator. Safety assessments will be performed at scheduled intervals from Day -2 through the end of study assessment as presented in the study schedule of assessments ([Table 12-1](#)). Assessment windows are presented in [Table 12-2](#).

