#### 16.3. LABORATORY EVALUATIONS

Central laboratory results will be included in the reporting of this study for hematology, clinical chemistry (including liver function) and urinalysis. A list of laboratory assessments to be included in the outputs is included in Table 6-1 of the protocol. Assessment windows for laboratory evaluations are presented in Table 12-2 of the protocol. Presentations will use SI units, as provided by the laboratories.

Protocol-specified clinical laboratory tests will be summarized using descriptive statistics.

Clinical laboratory data collected during study conduct which were not required per protocol, such as for special testing to evaluate an AE, will be listed separately and not summarized.

Quantitative laboratory measurements reported as "< X", i.e. below the lower limit of quantification (BLQ), or "> X", i.e. above the upper limit of quantification (ULQ), will be converted to X for quantitative summaries, but will be presented as recorded, i.e. as "< X" or "> X", in the listings.

The following summaries will be provided for laboratory data by cohort at each scheduled timepoint:

- Actual and change from baseline (descriptive statistics n, mean, SD, median, minimum and maximum for quantitative measurements; frequency and proportion for categorical measurements)
- Shift from baseline (normal, low, high) to last observation on treatment (continuous

Author: [name]

1.0

Version Date: 25 April 2019

Version Number:

Template No: CS\_TP\_BS016 – Revision 5 Reference: CS\_WI\_BS005

Effective Date: 01Apr2018

Palladio Biosciences STATISTICAL ANALYSIS PLAN: PROTOCOL PA-102 Page 26 of 36

variables only)

- Individual data listings of laboratory results, with values outside the laboratory's
  reference range flagged as low or high. Clinical laboratory reference/normal ranges
  will be included in the listing.
- For urinalysis, shift tables comparing baseline value to maximum value (using number of subjects with results of negative, trace or positive) for categorical variables
- A listing of serum and urine pregnancy results.

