### 16.4. ECG EVALUATION

Results of the ECG assessments will be included in the reporting of this study. Overall evaluation of safety ECGs will be summarized by cohort using descriptive statistics as described in Section 6.1, as well as with frequency counts and percentage of subjects with results classified by the investigator as normal, abnormal – not clinically significant (NCS) and abnormal – clinically significant (CS).

The following ECG parameters will be reported for this study: PR interval, QRS duration, QT

Document: \\leedc-vnasc01\BIOSdata\Palladio\Lixivaptan\\WYA34000\Biostatistics\Documentation\SAP\PA-

102 SAP V1.0 NonPKPD 25APR2019

Author: [name] Version Number: 1.0

Version Date: 25 April 2019

Template No: CS\_TP\_BS016 – Revision 5 Reference: CS\_WI\_BS005

Effective Date: 01Apr2018

Palladio Biosciences STATISTICAL ANALYSIS PLAN: PROTOCOL PA-102 Page 27 of 36

interval (uncorrected), QTcF interval, and heart rate and ventricular rate (beats per minute (bpm)). Values will be obtained directly from the eCRF and no derivations are required.

Assessment windows are presented in Table 12-2 Appendix 3 of the Protocol.

The following summaries will be provided for ECG data for each cohort over each scheduled timepoint:

- Actual ECG parameter values (descriptive statistics for quantitative measurements)
- Shift from baseline interpretation to the investigator interpretation at each time point
- Incidence of abnormal criteria (frequency counts and percentage of subjects as normal/abnormal NCS/abnormal CS)
- · Listing of subjects' individual ECG results

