### 16.5. VITAL SIGNS

The following vital signs measurements will be reported for this study:

- Sitting systolic blood pressure (SBP) and diastolic blood pressure (DBP) (mmHg)
- Pulse rate (beats/minute)
- Respiratory rate (breaths/min)
- Temperature (°C).

The following summaries will be provided for vital signs data at each scheduled timepoint by cohort for the Safety Analysis set using descriptive statistics:

Actual and change from baseline

Incidence of markedly abnormal values

Document: \\ieedc-vnasc01\BIOSdata\Palladio\Lixivaptan\\WYA34000\Biostatistics\Documentation\SAP\PA-

102 SAP V1.0 NonPKPD 25APR2019
Author: [name]

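### Non-PK/PD SAP 6.4 assigns unscheduled readings to worst-case and outlier assessment, but the vital-sign and ECG tables in 16.4 and 16.5 have no row in which to count them

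*SAP*

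**What the plan says.** **General rule.** Non-PK/PD SAP 6.4 excludes unscheduled measurements from summary statistics but says that they "will contribute to the best/worst case value where required (e.g., shift tables) and assessment of clinical outliers". When a scheduled assessment is retested, "the last available measurement for that scheduled time (i.e., the retest measurement) will be used for summaries unless flagged as invalid". It adds: "Listings will include all scheduled, unscheduled, retest and early discontinuation data".

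**Vital signs.** SAP 16.5 introduces its tables with "The following summaries will be provided for vital signs data at each scheduled timepoint by cohort". One item under that lead-in is "Incidence of markedly abnormal values", judged against the limits in Table 4 (16.5.1). The shift against the Table 3 normal limits is from baseline to all visits.

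**ECG.** SAP 16.4 uses a similar lead-in: "The following summaries will be provided for ECG data for each cohort over each scheduled timepoint". The shift in investigator interpretation is given at each time point.

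**Laboratory.** SAP 16.3 says that data not required by the protocol, "such as for special testing to evaluate an AE, will be listed separately and not summarized". The same section has a urinalysis shift from baseline to the maximum value, and a shift for continuous analytes to the last on-treatment observation.

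**Source of extra readings.** Protocol 6.1 states: "Additional safety assessments may be performed as needed at the discretion of the Investigator". Protocol 6.1.3 allows a confirmatory repeat of vital signs, and 6.1.5 calls for confirmatory laboratory tests of clinically significant abnormalities.

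**The concern.** Vital signs and ECG are part of the primary safety endpoint (protocol 2.2.1) and of the primary estimand (Non-PK/PD SAP 7.2). Section 6.4 gives unscheduled readings a role in worst-case and outlier assessment, yet the vital-sign and ECG specifications do not say where that role is carried out.

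The schedule makes this matter more than usual. On treatment, blood pressure and pulse are scheduled before doses given in the CRU and at Day 8 discharge (protocol Table 12-1, footnote 8). Only one scheduled ECG follows the start of dosing, on Day 8 (footnote 7). Protocol 1.6 names dizziness, orthostatic hypotension and tachycardia among the most common adverse events with this drug. A reading prompted by such a symptom may be the only one taken near it, and it is the kind of reading that 6.4 sets apart.

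Two further effects work on the same tables. Under the retest rule a normal repeat displaces the abnormal original in summaries. And an incidence table split by timepoint does not show how many of the 8 subjects in a cohort were ever markedly abnormal.

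**Working it through.** The main point is textual, and the plan has no figure to reproduce.

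**1. Does each table have a place for the 6.4 worst-case or outlier rule?**

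| Output | SAP section | Unit of tabulation | Clear place for the rule |
|---|---|---|---|
| Markedly abnormal vital signs (Table 4) | 16.5, 16.5.1 | Scheduled timepoint | No |
| Vital-sign shift (Table 3) | 16.5 | Visit | No |
| ECG interpretation shift | 16.4 | Time point | No |
| ECG abnormal incidence | 16.4 | Scheduled timepoint | No |
| Urinalysis shift | 16.3 | Baseline to maximum | Yes |
| Continuous laboratory shift | 16.3 | Baseline to last on-treatment value | No (last, not worst) |

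That is 0 of 2 for vital signs, 0 of 2 for ECG and 1 of 2 for laboratory shifts. Table 4 holds the only outlier thresholds in this SAP.

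**2. Could an off-schedule reading be assigned to a visit?** SAP 6.5 performs no visit windowing. The visit list in Appendix 1 has no unscheduled, worst-value or early-termination entry. That list is weak evidence by itself: it also omits Days 2, 4 and 6, on which vital signs are scheduled, so it may not be complete.

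**3. What happens to a repeat?** If an original systolic pressure meets the Table 4 limit of 80 mmHg or less and the repeat does not, 6.4 puts the repeat in the summary. Section 6.4 does not say whether the displaced original still counts as a worst case.

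**4. Scheduled blood-pressure and pulse timepoints after first dose, to Day 8** (protocol Table 12-1, footnote 8 and dosing rows): Day 1 PM, Day 2 AM, Day 4 AM, Day 6 AM, Day 6 PM, Day 7 AM, Day 7 PM and Day 8 discharge.

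1 + 1 + 1 + 2 + 2 + 1 = 8

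Respiratory rate and temperature have only Day 8 and End of Study after dosing, so splitting by timepoint mainly affects blood pressure and pulse.

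**5. Illustrations for one cohort of 8** (the patterns are assumed, not predicted):

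- One subject markedly abnormal only at an unscheduled time: every scheduled row shows 0/8 = 0.0%. A worst-value row shows 1/8 = 12.5%.
- Two such subjects: 0/8 against 2/8 = 25.0%.
- Three subjects, each abnormal once at a different scheduled time: three rows of 1/8 = 12.5%. Counted once per subject, 3/8 = 37.5%.

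The first two illustrate the unscheduled-reading gap. The third is a separate matter of pooling scheduled rows.

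**The case against.** A reader might infer that readings taken because something was wrong reach only the listings. The documents do not support that:

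- Retests enter the summaries (6.4).
- Unscheduled readings can set the baseline (6.3).
- The urinalysis baseline-to-maximum shift can use unscheduled values.
- The symptom that prompted the reading is itself reportable whatever its clinical significance (protocol 6.1.9.1), so it appears in the TEAE tables.
- A value judged clinically significant is recorded as an AE (SAP 16.1).

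Often, then, only the numerical value is left untabulated. That limits the loss but does not remove it. Table 4 applies fixed thresholds that do not depend on investigator judgment, and the AE route does depend on it for the value itself.

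A reader might also infer that 16.3 contradicts 6.4. It does not clearly do so. It sets aside tests the protocol did not require, while protocol 6.1.5 itself calls for confirmatory tests (leaving creatinine and sodium to discretion). What is unclear is whether an extra result for a Table 6-1 analyte counts as not required.

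The strongest objection is that the scheduled-timepoint lead-in is loose. In 16.3 similar wording also covers listings and the baseline-to-maximum shift, and in 16.4 it covers the individual ECG listing. Section 16.5.1 has no scheduled-only limit, so 6.4 could be read as governing Table 4. That reading is available, but it is not stated. Two programmers could build different incidence tables from the same text.

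Finally, SAP 8.2 refers to output templates that are not among the documents reviewed. They may already contain such a row, so the point is confined to the SAP text.

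**Conclusion.** The concern holds as a gap between 6.4 and the table specifications in 16.4 and 16.5. As written, an abnormal unscheduled reading, or an abnormal original followed by a normal retest, may not be counted in the markedly abnormal incidence, the vital-sign shift or the ECG tables. Each affected subject would change a cohort count by 1/8, or 12.5 percentage points. The blood-pressure and pulse incidence is also spread over 8 post-dose timepoints with no subject-level total.

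How often this will happen cannot be derived from the documents. A reader might try to size it by assuming a 1% to 5% chance of a markedly abnormal value at each of the 8 readings: 1 - 0.99^8 = 7.7% to 1 - 0.95^8 = 33.7%. Those rates are assumed and the readings are treated as independent. More importantly, the calculation describes pooling of scheduled rows, so it does not measure the effect of leaving out unscheduled readings.

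For ECG, the single scheduled post-dose recording already counts each subject once. A worst-case row there adds only repeat, unscheduled and early-termination recordings.

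The study is descriptive, SAP 16 plans no statistical comparison of safety data unless otherwise specified, and all readings are listed. This is therefore a low-cost improvement to the summary of a primary safety endpoint, not a flaw that invalidates the analysis.

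**What to change.** **Non-PK/PD SAP 16.5 and 16.4.** Add one row: worst value after first dose to Day 8 or early termination, including scheduled, repeat and unscheduled readings, counted once per subject. Put it in the Table 4 incidence table and in the vital-sign and ECG-interpretation shift tables. For vital signs, count the low and high directions separately, because one subject may meet both. For ECG, rank the interpretation as normal, abnormal NCS, abnormal CS. Keep the existing scheduled-timepoint rows.

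**Non-PK/PD SAP 16.3.** State that extra on-treatment results for analytes in protocol Table 6-1 follow 6.4, and that only tests outside that panel are listed without summary.

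**Cost.** A SAP wording change and one extra row in existing outputs, with no new data and no change to trial conduct. The downside is that subjects measured more often have more chances of an extreme value, so the new row should be read beside the scheduled-timepoint rows.

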6.1.3 Vital Sign Measurements

Vital sign measurements will include systolic blood pressure, diastolic blood pressure, pulse rate, respiration rate, and body temperature and will be performed at the timepoints specified

in the study schedule of assessments (Table 12-1). Assessment windows are presented in Table 12-2.

Subjects will remain at rest in a seated position for a minimum of 5 minutes before vital sign measurements are obtained. For all subjects, blood pressure and pulse rate will be measured using an automated sphygmomanometer. A confirmatory repeat vital sign measurement may be performed at the discretion of the Investigator. If other procedures are scheduled at the same timepoint, vital signs will be obtained first, before an ECG and/or blood draw.

6.1.4 12-Lead Electrocardiograms

Electrocardiogram parameters of heart rate, ventricular rate, PR interval, QRS duration, QT interval (uncorrected), and QT interval corrected for heart rate according to Fridericia's formula (QTcF) will be performed at the timepoints specified in the study schedule of assessments (Table 12-1). Assessment windows are presented in Table 12-2.

Electrocardiograms will be obtained with the subject remaining in a supine or semi-recumbent position following 5 minutes of rest. All electrocardiograms throughout the study for a given subject should be measured in the same position, i.e. either all in a supine position or all in a semi-recumbent position. If other procedures are scheduled at the same timepoint, the ECG should be obtained after vital sign measurements and/or before the scheduled blood draw.

For all subjects, ECGs will be reviewed, signed, and dated by the Investigator or a qualified designee. The ECGs will be classified as being one of three categories: normal, abnormal but not clinically significant (NCS), or abnormal and CS. All CS findings will be reported as AEs.

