6.1.5 Clinical Laboratory Tests

Blood and urine specimens will be collected for the clinical laboratory (hematology, clinical chemistry, and urinalysis), pregnancy tests (all female subjects) and FSH tests (if necessary for postmenopausal female subjects) at the timepoints specified in the study schedule of assessments (Table 12-1). A confirmatory assessment should be obtained as soon as possible for any clinically significant abnormal laboratory parameter. Mild elevations in serum creatinine or serum sodium are known pharmacodynamic effects of vasopressin antagonists like lixivaptan, therefore confirmatory assessments for serum creatinine and serum sodium will be at the Investigator's discretion.

Assessment windows are presented in Table 12-2. Clinical laboratory parameters for analysis are presented in Table 6-1.

Table 6-1 Clinical Laboratory Parameters

Chemistry Panel	Hematology	Urinalysis
Alanine aminotransferase*	Hematocrit	pH
Albumin	Hemoglobin	Specific gravity
Alkaline phosphatase*	Red blood cell count	Protein
Aspartate aminotransferase*	Quantitative platelet count	Glucose
Bilirubin Total and Direct*	White blood cell count	Ketones
Blood urea nitrogen	with differential (total and %):	Bilirubin
Calcium	Neutrophils	Blood
Chloride	Lymphocytes	Nitrite
CO ₂	Monocytes	Urobilinogen
Creatinine	Eosinophils	Leukocyte esterase
Gamma-glutamyl transferase*	Basophils	Microscopic examination (if positive blood, nitrite, leukocyte esterase, or protein)
Glucose		
Phosphorous	Other Tests	
Potassium	Urine or serum pregnancy test	Urea
Protein	(female subjects)	Creatinine
Sodium	FSH (if necessary for	Sodium
Urea	postmenopausal female subjects)	
Uric acid		

Abbreviations: CO₂ = carbon dioxide; FSH = follicle-stimulating hormone.

*Liver function testing

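### A retest replaces a valid scheduled value in summaries, and the only laboratory retest the protocol calls for follows an abnormal result, so by-visit laboratory tables are pulled toward normal

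*SAP*

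**What the plan says.** Section 6.4 of the non-PK/PD SAP has three rules.

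- **Retests:** "the last available measurement for that scheduled time (i.e., the retest measurement) will be used for summaries unless flagged as invalid". As worded, the invalid flag applies to the retest. Whether the first value was valid plays no part.
- **Unscheduled measurements:** "Unscheduled measurements will not be included in summary statistics but will contribute to the best/worst case value where required". The section gives shift tables as an example and adds the assessment of clinical outliers.
- **Listings:** "Listings will include all scheduled, unscheduled, retest and early discontinuation data".

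Section 6.4 of the PK/PD SAP repeats the retest and listing rules. It leaves post-baseline unscheduled values out of summary statistics and has no worst-case clause.

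The protocol says when a repeat is taken. For laboratory tests (6.1.5): "A confirmatory assessment should be obtained as soon as possible for any clinically significant abnormal laboratory parameter". Because mild rises are expected with this drug class, "confirmatory assessments for serum creatinine and serum sodium will be at the" Investigator's discretion. For vital signs (6.1.3): "A confirmatory repeat vital sign measurement may be performed at the discretion of the Investigator". Neither section calls for repeating a normal result.

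The affected outputs are in the non-PK/PD SAP. Section 16.3 gives laboratory descriptive statistics, including minimum and maximum, at each scheduled timepoint, and a table of "Shift from baseline (normal, low, high) to last observation on treatment". Section 16.5 lists "Incidence of markedly abnormal values" among the vital-sign summaries at each scheduled timepoint.

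**The concern.** If the decision to repeat depends on the first result, and the repeat then takes its place, the summarised data are filtered on the outcome. A high value partly due to within-subject variation will on average be lower when repeated, and there is no matching process that raises normal values. Tables built from the filtered values show fewer and smaller excursions than the scheduled samples did.

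Timing may add to this. Section 6.5 of the non-PK/PD SAP applies no visit windowing, so no limit is stated on how late a retest may be and still stand in for the scheduled value. The protocol (3.1.1 and 4.2.1) describes creatinine rises as transient and reversible, so a late repeat, if the investigator takes one, could put a recovering value in place of an on-drug one.

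Laboratory findings and vital signs are among the primary endpoints (Protocol 2.2.1) and the variables of the primary safety estimand (non-PK/PD SAP 7.2). The analysis is descriptive, so these tables are themselves the result.

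**Working it through.** **Inputs from the documents.** Cohort size is 8. Non-PK/PD SAP Table 2 gives the probability of not observing an AE in 8 subjects: 0.43 at a true rate of 0.10 and 0.168 at 0.20.

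**Inputs assumed, because the documents give none.** The correlation ρ between original and retest is 0.6 to 0.8. Values are normal with common variance. A retest is taken whenever the original exceeds 1.96 SD, high side only. The share r of abnormal originals that read normal on retest is 25%, 50% or 75%.

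**1. The plan's own figures.** (1 − p)^8 gives 0.9^8 = 0.4305 and 0.8^8 = 0.1678, agreeing with Table 2.

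**2. Share of abnormal values in a by-visit table.** Without replacement it is P(X > 1.96) = 2.5%. Under the rule, a value stays abnormal only if original and retest both exceed the cut, so the share is P(X > 1.96 and Y > 1.96) for a bivariate normal pair.

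| Drug shift | No replacement | ρ = 0.6 | ρ = 0.8 |
|---|---|---|---|
| None | 2.5% | 0.6% | 1.1% |
| 1 SD | 16.9% | 7.9% | 10.5% |

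With no shift, about 25% to 44% of the abnormal values remain in the table. With a 1 SD shift, about 47% to 62% remain.

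**3. Mean.** With no drug shift, the change is −(1 − ρ)φ(1.96), where φ(1.96) = 0.0584.

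- ρ = 0.6: −0.4 × 0.0584 = −0.023 SD
- ρ = 0.8: −0.2 × 0.0584 = −0.012 SD

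The standard error of a mean of 8 is 1/√8 = 0.354 SD, so this is about 3% to 7% of one standard error. With a 1 SD shift the relevant density is φ(0.96) = 0.252, and the change is −0.05 to −0.10 SD. If high and low values trigger repeats equally, the mean does not move, but abnormal counts and the SD still fall.

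**4. What this does to a table of 8.** If a share r of abnormal originals normalises, the rate visible in the table is p(1 − r), and the chance that the table shows none is (1 − p(1 − r))^8.

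| True rate p | r = 0 | r = 25% | r = 50% | r = 75% |
|---|---|---|---|---|
| 0.10 | 0.430 | 0.536 | 0.663 | 0.817 |
| 0.20 | 0.168 | 0.272 | 0.430 | 0.663 |

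These figures describe an abnormal-value category in a by-visit table. They do not describe AE tables, which section 6.4 does not touch.

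**5. Whether other rules restore the replaced value.**

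- The worst-case clause names unscheduled measurements; it does not say that a replaced original still counts.
- The laboratory shift table takes the last on-treatment observation, not the worst. If that observation was retested, the retest sets the category.
- Markedly abnormal vital signs are reported by scheduled timepoint, where the retest stands in.
- The PK/PD SAP has no worst-case clause.

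**The case against.** The strongest reply is that the plan catches important values elsewhere. A laboratory result that must be confirmed is one judged clinically significant, and such results are to be recorded as AEs or SAEs (Protocol 6.1.9.3; non-PK/PD SAP 16.1) with no requirement that a repeat confirm them. They therefore reach the AE tables, and the listings keep both values and flag those out of range. With 32 subjects the listings can be read in full. This stands. A reader might infer that the primary safety results as a whole are biased, or that one replacement could erase the only sign of a problem. The documents do not support that.

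A second reply concerns the trigger. A reader might infer that only extreme values are ever replaced. The protocol text does not go so far: vital-sign repeats have no stated threshold, and creatinine, from which eGFR is calculated, is exempt from the standing instruction to confirm. The pull toward normal is therefore documented for the remaining laboratory tests and only possible for creatinine, sodium, vital signs and PD endpoints.

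Third, the protocol says confirmatory assessment, while the SAP speaks of retests and unscheduled measurements without separating them. If confirmations were treated as unscheduled, the original would stay in the summaries. That is a fair reading, but it shows a gap: two programmers could build different safety tables from the same data.

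Fourth, a replaced Day 2 value would not normally reach the last-on-treatment shift table under either rule, and the urinalysis shift uses the maximum. So the shift-table effect is limited to a retested last on-treatment observation.

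Finally, the rule is prespecified, is the same in every cohort and feeds no formal between-group comparison. That is true, but it does not make the maxima or abnormal counts right.

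**Conclusion.** The point holds in a limited form. Followed as written, section 6.4 discards valid scheduled values in favour of retests, and the one standing instruction to retest is an abnormal laboratory result. Laboratory maxima, counts of abnormal values and any retested last-on-treatment shift category move toward normal. Vital-sign and PD tables may do so too, depending on how investigators use their discretion.

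The effect on means is small: about 0.01-0.02 SD with no drug shift. The effect on abnormal counts could be large: from 2.5% to about 0.6-1.1% at the 1.96 SD cut. Both results rest on assumed correlations of 0.6-0.8 and an automatic one-sided trigger, which is not the protocol's own, and on confirmations being handled as retests. With no drug effect, the drop is a loss of within-subject variation and should not be read as a demonstrated loss of safety signal. The actual size cannot be found from the documents.

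The change should be made, because the tables are the descriptive result and the correction costs little.

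**What to change.** In section 6.4 of both SAPs:

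1. Use the original scheduled value in by-visit summaries and shift tables unless it is flagged invalid (for example, a haemolysed or mislabelled sample). Use the retest only in that case.
2. Define a retest and an unscheduled measurement, and say which of them a confirmatory assessment under Protocol 6.1.5 or a repeat under 6.1.3 is.
3. State that originals and retests both count in worst-case, markedly abnormal and maximum-value outputs. In the PK/PD SAP this sentence is new.

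The cost is a few sentences per SAP and the matching programming. No new data are needed, since both values are already to be listed. The downside is that safety tables will look slightly less favourable.
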